## 10. HUMAN SUBJECTS

We will recruit 255 participants in the according to the table below, with Year 5 for completing interventions, follow-up assessments, and the implementation component of the project.

Recruitment Goals and Number of Contacts (i.e., Intervention and Assessments)					
	Year 1	Year 2	Year 3	Year 4	Year 5
CBT2go Intervention Condition	15	23	24	23	0
EMA-Only Condition	15	23	24	23	0
Standard Care Condition	15	23	24	23	0
Total In-Person Contacts/year	180	276	288	276	138

Complete Inclusion/Exclusion Criteria are as follows:

Participants in this study will be included if: male or female, any race/ethnicity and age 18-65; have a DSM-IV-TR diagnosis of BD, SZ, or schizoaffective disorder based on the MINI; minimum level of impairment on at least one of the target outcomes, defined as a score of  $\geq 3$  on the BPRS depression, mania, hallucinatory behavior, or asociality items; current outpatient participation in

routine psychiatric care and on stable medications, defined as the same regimen for at least 60 days and a constant therapeutic dose for at least 30 days; willing to sign a release of information form in order for study staff to be able to inform treating clinicians of symptom exacerbations/suicidality; able to speak and read English ; and capable of and willing to provide signed informed consent and pass the UBACC test for decisional capacity for research (see below).

Participants will be excluded if: diagnosis of dementia or past head trauma with loss of consciousness for > than 30 minutes; cannot complete the assessment battery; visual acuity (assessed with Snellen chart) and manual dexterity sufficient to navigate a touch screen device.

### **INCLUSION OF WOMEN AND MINORITIES**

According to the 2010 US Census, for adults in San Diego County, 47% were male and 71% were Caucasian. We will strive to achieve a similar sample composition, so that the data will generalize to the larger population. In our preliminary studies, the proportion of patients who identified as Caucasian was 72% and the proportion of men was 52%. Notably, our sample ascertainment for the proposed study will be more likely to include members of ethnic minorities, as we will be recruiting directly and exclusively from the San Diego County Mental Health System. As described in a recent Annual Report of San Diego County Mental Health (viewable at

[http://www.sdcounty.ca.gov/hhsa/programs/bhs/documents/AMHS\\_0809.pdf](http://www.sdcounty.ca.gov/hhsa/programs/bhs/documents/AMHS_0809.pdf)), a total of 48% of system users were members of ethnic minority groups (Hispanic/Latino, 19%; African-American, 12%). The gender distribution of San Diego County Mental Health users was evenly divided among men and women. Therefore, we anticipate being able to recruit an ethnically diverse sample with equal proportions of men and women. Neither gender nor ethnicity will be a criterion for inclusion or exclusion of subjects. We will continuously monitor the gender distribution for this study, as well as the ethnicity characteristics of the sample as it accrues. We will keep all research assistants and referral sources informed regarding our progress and our current priorities for recruitment of women and minorities. Thus, we plan to have an ongoing process through which we ensure that women and minorities are included and appropriately represented.

### **INCLUSION OF CHILDREN**

We will include children between the ages of 18 and 21. Patients younger than 18 will not be included, since the use of such subjects would require modification of the neuropsychological battery, psychiatric interview and functional assessments, thereby substantially changing the research design. Further, the functional abilities of individuals under the age of 18 tend to be different than those of adults and expectations regarding the type and nature of social interactions, independent living, and financial self-support are notably different under the age of 18.

## **11. RECRUITMENT**

Recruitment of participants and informed consent procedures will follow established methods in previous ACISIR studies. The referral sources for this study will be the clinics and other outpatient service sites of the San Diego County Adult and Older Adult Mental Health System (AOAMHS), which serves over 43,000 persons per year (see Resources). Our recruitment efforts will include community clinics with mental health clinics throughout the San Diego County AOAMHS that serve primarily Hispanic and African American populations. Participants will be recruited by a variety of methods, including direct referrals from providers, posted flyers and informative brochures, staff in-services and community outreach meetings. These recruitment methods have been honed in our long-standing academic-community partnership with the San Diego County Mental Health System as described in our previous publications

Upon contact with staff, potential participants will undergo a brief telephone screening interview (or in-person in rare cases), during which the Project Manager will introduce the study and review the inclusion/exclusion criteria and study procedures. If the participant is appropriate for inclusion into the study and interested in participation, a staff member will describe the requirements of the study, including questionnaires, assessments, and randomization to interventions. In all cases, fully informed consent will be obtained and [name] and other co-investigators will be directly available to answer questions, should any be raised by the participant.

BD participants who have been randomized to the EMA-only condition who have indicated on their consent that they are willing to learn about participating in additional procedures (blood draws and home visits for the first 2 weeks) will be approached at their single in-person session to undergo the consent process for these assessments.

## **12. INFORMED CONSENT**

Individuals are provided with a copy of the consent document and a copy of the Experimental Subject's Bill of Rights. Potential participants are encouraged to ask questions throughout this process. Those who are eligible are fully informed and consented for the full study and provided with a copy of that consent documentation. All research subjects are informed regarding applicable HIPAA protections and sign a separate HIPAA document. To enhance comprehension, the informed consent documents are written at the 8th grade level of language. All participants will be informed of the possibility of additional compensated procedures for an eligible subset of participants, and will be asked to indicate their interest in learning about these home visits and blood draws (described above). Informed consent will be documented with the IRB-approved written consent form that each participant will sign prior to participation. Signed and witnessed consent forms will be kept on file in a specially secured cabinet.

Our screening protocol contains a direct assessment of decisional capacity, in light of the elevated base rate of cognitive impairment among participants with bipolar disorder or schizophrenia that can lead to diminished capacity to understand, appreciate, and apply sound reasoning in the decision to participate in research. In order to ensure that all participants have adequate decisional capacity to participate in this research study, we will administer the University of California San Diego Brief Assessment of Capacity to Consent (UBACC), which is a 10-item questionnaire that is tailored to the specific procedures of the study. This measure queries participants about the basic procedures, risks, benefits, and purpose of the study, along with participant rights.

If a potential participant is unable to achieve a perfect score on the first or second administration of the quiz or if there is any other reason to suspect that the individual may lack the capacity to give informed consent because of decisional impairment, that individual is assessed by a study clinician. The final determination regarding decision-making capacity is made by the clinician and documented in the research record. If an individual is unable to demonstrate the capacity to consent as detailed above, the individual will be excluded from the present study.

## **13. ALTERNATIVES TO STUDY PARTICIPATION**

Participating in the study will not alter participant's care. For participants who are interested we will provide referrals to them for community mental health providers and the free depression bipolar support group held weekly at the VA Hospital. Alternative to study participation is to not participate in this study.

## **14. POTENTIAL RISKS**

**Assessment:** The interviews, questionnaires, computer-based assessments, and neuropsychological tests are non-invasive clinical assessments associated with minimal risk. All measures are physically non-invasive, have been used in prior studies with seriously mentally ill participants, and have been found to elicit minimal distress and discomfort. Nevertheless, participation in the psychosocial evaluation and responding to questions on the mobile device will require time and attention. Some participants may become bored or fatigued completing the evaluation. Some participants may also become distressed during the psychiatric evaluation, which requires them to discuss their current symptoms, as well as the history of their symptoms.

**Intervention:** Risks involved in participating in this intervention are minimal. During the Baseline assessment and follow-up assessments, participants may experience feelings of anxiety or discomfort while talking about themselves and/or symptoms. Participants may also become fatigued by filling out questionnaires or answering questions in person, or, if they are randomized to the experimental conditions that involve mobile devices, on the device.

**Confidentiality:** As with any intervention study, a risk of disclosure of personal material exists.

**Blood Draw:** A subset of interested subjects in the EMA-only condition will be asked to give 3 blood samples over the course of their participation. For most individuals, needle punctures for blood draws do not cause any serious problems. However, there is a small risk of bleeding, bruising, discomfort, infections and/or pain at the needle site or dizziness.

## 15. RISK MANAGEMENT PROCEDURES AND ADEQUACY OF RESOURCES

**Assessment:** During in-person interviews, trained raters will closely monitor for signs of stress, fatigue, and distress. Rest breaks will be provided as needed during all assessments to reduce fatigue and boredom. Also, subjects may refuse to answer any specific questions or to complete any given tests. We provide snacks, water and recommend breaks to participants if they report feeling fatigue. We also provide participants the option of splitting the assessments, particularly the baseline assessment which is longer than the other assessments, on different days. They will also be advised that they can withdraw from the study at any point and can still receive the compensation. If a participant discloses that he or she is experiencing suicidal ideation during diagnostic interviewing or on standard clinical measures, the rater will immediately contact the PI to ensure that steps are taken to ensure the participant's safety. The two measures that directly elicit information about current suicidal thoughts are the Columbia Suicide Severity Rating Scale and the Scale for Suicide Ideation. Any report of ideation on these instruments that exceeds "none" will result in an immediate contact to the PI to ensure participant safety. These steps will include a formal risk assessment and may lead to contacting the participant's providers (with signed consent to do so) and arranging emergency care for the participant. Our research center has a Clinical Response Team (of which the PI is the Associate Director) that will provide additional back-up; this team includes board-certified psychiatrists and psychologists who will be available and on site at all times.

**In-Person Session (CBT2go):** The Project Therapist will receive intensive training from supervising psychologists and will be provided supervision on a weekly basis by [name]. Participants will be closely monitored and additional (in session) assistance will be provided to those participants experiencing frustration or distress. Should a participant be observed to be exhibiting an acute symptom exacerbation and/or suicidal or homicidal ideation, the Project Therapist member will notify Drs. [name] or [name] immediately and they will conduct a formal evaluation of the participant with

additional back-up from the Clinical Response Team. Given that all participants must be currently participating in stable outpatient care, the need for immediate emergency services will be unlikely. Nevertheless, based on our experience conducting clinical research in serious mental illness, we have developed the above plan to intervene appropriately should such a need arise.

**Experimental Conditions (Week 1 through Week 12):** Participants in the CBT2go and EMA-only conditions will be provided a smart-phone device with which to answer questions about their mood, activities and contexts. After baseline interview (and in-person session if in the CBT2go condition), participants will be asked to respond to questionnaires on the device until Week 12. Participants in the Standard Care condition will not be provided a device. We have taken several steps to ensure participant safety during the periods of no in-person contact. All participants will be provided with staff contact information and emergency resources in a printed manual, and they will be instructed that they may call the PI or project manager at any time in case of questions or emergencies. Participants must provide release of information for our staff to contact treating psychiatrists or other appropriate healthcare provider, so any emergent crises will be relayed to that participant's provider. In the CBT2go and EMA-only condition, responses at the severe spectrum of the mood or voices scales are accompanied with a screen that instructs participants to contact both emergency services (911 can be directly accessed via the device) AND project staff, if in crisis. We will monitor these protocols during the course of the study and will make adjustments to inclusion/exclusion criteria in case of adverse events.

**Data and Safety Monitoring Board:** The study will be reviewed annually through the UCSD DSMB. The board consists of non-UCSD faculty in psychiatry, community members, and bioethicists.

**Blood Draw:** Blood samples will be drawn only by research staff trained and certified in phlebotomy. Staff will take care to assure the participant is comfortable and participants will be provided with the necessary medical equipment (e.g. band-aids) to care for any irritation at the site of the blood draw.

#### **16. PRIVACY AND CONFIDENTIALITY CONSIDERATIONS INCLUDING DATA ACCESS AND MANAGEMENT**

**Confidentiality:** In order to protect confidentiality, all participant data will be de-identified by assigning each participant a unique ID in computer files, and all physical files from the study will be kept in a locked cabinet in our offices at the Stein Clinical Research Building at UCSD. All electronic data and files will be stored on a secure server. Only study investigators and personnel will have access to these data. All documentation will identify participants only by their Unique ID number and not other personally identifying information.

On the device, participant data is not stored locally and cannot be accessed by anyone if the device is lost or stolen. Data are encrypted upon transfer to our server and linked by unique ID that is de-identified. Since we will be providing the devices to participants, there is no risk of loss of confidentiality associated with access to personal telephone numbers. Should the participants lose the device, we have taken the additional step of incorporating the Auto wipe application on all study devices which enables remote factory reset of the device, erasing all data. If participants lose or damage the device, they will not be held responsible for the cost of the device or any other costs.

#### **Data and Safety Monitoring Plan**

Data safety will be of utmost importance in this project. Data will be coded by subject number only and will be filed in locked file cabinets in locked staff offices. In addition, signed consent forms will be filed in a separate location from the raw data. A codebook linking subject identifying information with

subject number will be kept on a computer that is password protected and, within that, a file that is password protected.

Adverse events in this research project are expected to be extremely rare. However, we have established plans for resolving any adverse event should one occur. First, during screening for the project, trained research personnel will assess (using standardized screening tools) for any serious medical or psychological conditions that may require immediate medical attention or psychiatric treatment. The rationale for this is because the presence of serious medical or psychiatric conditions would make these individuals inappropriate for the proposed research study. Should attention be required, staff will provide these individuals with information about suitable referrals, including local hospitals, clinics, and/or relevant health-care and mental health professionals, and they will strongly encourage the individuals to follow up with these referrals.

Second, UCSD's IRB requires regular updates on the status of research projects, including the number of participants enrolled, adverse events or unanticipated problems, number of withdrawals from the project, complaints about the research, and any protocol changes. The IRB also monitors the consent forms and ensures that appropriate HIPAA information is included.

Third, the Data and Safety Monitoring Board of the Research Center will review the project yearly.

Taken together, use of these methods should allow for adequate evaluation of, and response to, both potential enrollees and actual participants.

#### **17. POTENTIAL BENEFITS**

As these are experimental interventions, there may be no direct benefit to participants. However, benefits to the individual participants may include decreased emotional distress and improved functioning from cognitive and behavioral changes facilitated by the interventions. Participants may gain an increased understanding of the role thoughts and behaviors play in the symptoms of schizophrenia or bipolar disorder and may learn to reduce their symptoms by changing these thoughts and behaviors.

#### **18. RISK/BENEFIT RATIO**

The risks of this proposal are minimal. Protection of subject confidentiality and privacy are rigorously guarded by the assignment of coded numbers to each subject's data. Keys to these codes are stored in a locked file cabinet in the Stein Clinical Research Building. The dangers of adverse effects associated with this intervention are minimal. The benefits to the individual participants may be minimal, but may include decreased emotional distress from behavioral changes that they achieve. We judge the importance of knowledge resulting from this study and the potential for maximizing independence among psychiatrically stable individuals with bipolar disorder or schizophrenia to be quite significant; therefore, the risk to benefit ratio is low.

#### **19. EXPENSE TO PARTICIPANT**

There are no expenses to the participants. Participants will not be asked to pay for the device if it is lost or broken.

#### **20. COMPENSATION FOR PARTICIPATION**

Patients will be assessed (4-hour battery) at baseline, and a 2.5 hour testing battery at mid-point (6 weeks), post-treatment (12 weeks) and 3-month follow up (24 weeks) and paid \$70 for each assessment (there is no payment for treatment participation).

Participants will be provided a total of \$330 for completing all assessments – the compensation

structure is graded such that a \$50 bonus is provided for returning the device or attending all of the assessments. If the participant elects to drop out of the study, s/he will be offered the opportunity to return the equipment and complete assessment for \$50 compensation and will be notified that the mobile device will be deactivated remotely.

The SLOF questionnaire has three versions which are completed by the interviewer, the participant, and an informant of the participant. We will be providing informants with a small gift for completing the SLOF at each visit (baseline, 6 week, 12 week, and 24 week follow up). The gift will most likely be a small box of chocolates or some sort of snack valued less than 5 dollars

Those BD participants in EMA-only group who agree to participate in additional cognitive testing and blood draws over a 2 week period will be compensated an additional \$150.00. They will receive \$40.00 at the baseline visit, \$40.00 at home visit 1 and the remaining \$70.00 at home visit 2.

29. [name] DV, Palmer BW, Appelbaum PS, et al. A new brief instrument for assessing decisional capacity for clinical research. *Arch Gen Psychiatry*. Aug 2007;64(8):966-974.

23. FUNDING SUPPORT FOR THIS STUDY
NIMH Grant MHR01 100417; NIMH Grant Supplement MH 100417
24. BIOLOGICAL MATERIALS TRANSFER AGREEMENT
As described above, we will obtain three 5 ml blood samples from a subset of willing BD participants. Blood will be drawn into a blood collection tube and placed in a biohazard container for transportation. The staff phlebotomist will transport the specimen directly to [name] laboratory at UCSD immediately after visit completion and the blood samples will be stored at room temperature until assay.
25. INVESTIGATIONAL DRUG FACT SHEET AND IND/IDE HOLDER
Not applicable
26. IMPACT ON STAFF
There is no anticipated impact on staff at UCSD
27. CONFLICT OF INTEREST
None
28. SUPPLEMENTAL INSTRUCTIONS FOR CANCER-RELATED STUDIES
None
29. OTHER APPROVALS/REGULATED MATERIALS
Not applicable
30. PROCEDURES FOR SURROGATE CONSENT AND/OR DECISIONAL CAPACITY ASSESSMENT

There will be no surrogate consent obtained in this study.
 
Our screening protocol contains a direct assessment of decisional capacity, in light of the elevated base rate of cognitive impairment among participants with bipolar disorder or schizophrenia that can lead to diminished capacity to understand, appreciate, and apply sound reasoning in the decision to participate in research. In order to ensure that all participants have adequate decisional capacity to participate in this research study, we will administer the University of California San Diego Brief Assessment of Capacity to Consent (UBACC), which is a 10-item questionnaire that is tailored to the specific procedures of the study. This measure queries participants about the basic procedures, risks, benefits, and purpose of the study, along with participant rights.
 
If a potential participant is unable to achieve a perfect score on the first or second administration of the quiz or if there is any other reason to suspect that the individual may lack the capacity to give informed consent because of decisional impairment, that individual is assessed by a study clinician. The final determination regarding decision-making capacity is made by the clinician and documented

in the research record. If an individual is unable to demonstrate the capacity to consent as detailed above, the individual will be excluded from the present study.

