## 6. SPECIFIC AIMS

The goal of the study is to evaluate the effectiveness of a mobile real-time cognitive behavioral intervention for serious mental illness (SMI) and to identify the facilitators, barriers, and costs of implementation.

Our intervention called CBT2go builds on our extensive preliminary work using mobile devices, integrating ecological momentary assessment (EMA) with CBT content in BD and SZ. EMA is an ambulatory data collection technique that allows the *in vivo* assessment of moods, symptoms, medication adherence, social interactions and other daily activities. CBT2go delivers personalized thought challenging and behavioral coping interventions based on EMA's real-time reports. CBT2go is a 12-week intervention that involves a single in-person session followed by personalized yet automated responding on a mobile device, targeting affective and psychotic symptoms, medication adherence, socialization, and relapse prevention.

We are proposing a 6-month randomized controlled trial, with 255 participants recruited from the San Diego County public mental health system who have no current access to CBT. Participants will be stratified by diagnosis (BD or SZ), and will be randomized to receive CBT2go, EMA only, or Standard Care. This design will evaluate the added benefit of CBT components over EMA only (device contact, medication reminders, symptom monitoring), as well as the benefits of these components relative to Standard Care. Individuals will be assessed at baseline, mid-point (6 weeks), post-treatment (12 weeks) and 3-month follow up (24 weeks). Our primary and secondary outcomes will be measured with lab-based clinical ratings as well as EMA-based outcomes. We will also identify moderators (diagnostic group, cognitive ability) and mechanisms of change with respect to the elements of CBT

theory (changes in insight and dysfunctional attitudes). To inform pathways to implementation, we will evaluate the costs, barriers and facilitators to adopting CBT2go, with innovative methods from our implementation research. In addition, we would like to perform multiple blood draws on a subset of BD participants to determine whether variability in inflammatory markers, mood and cognitive performance predicts future suicide ideation in this population.

**Aim 1 (Effectiveness):** To determine the impact of CBT2go on primary and secondary outcomes.

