**Hypotheses 1 (Primary Outcome):** Compared to EMA and Standard Care, the CBT2go intervention will be associated with greater improvement in global psychopathology (as measured by BPRS Total Score).

**Hypotheses 2 (Secondary Outcomes):** Compared to EMA and Standard Care, the CBT2go intervention will be associated with greater improvement in EMA and standard lab-based measures of medication adherence, social functioning, and hospitalization and emergency service utilization.

**Aim 2 (Moderators and Mediators):** To determine the impact of moderators and mechanisms on outcomes.

**Hypothesis 3 (Cognitive Impairment and Diagnosis):** Neurocognitive ability will account for more variation in device compliance and treatment response than diagnostic group.

**Hypothesis 4 (Awareness and Attitudes):** Improvement in illness awareness and reduction in dysfunctional beliefs will mediate incremental benefit of CBT2go over comparison conditions.

**Exploratory Aim 3:** Explore a predictive model for suicidal ideation in bipolar disorder that includes direct and indirect effects of cognitive performance, inflammatory cytokine levels, and trajectories of negative affect.

**Supplement Aim 1: To evaluate the association between baseline trait and dynamic impulsivity/social threat with lifetime suicide risk and intensity of and intra-individual variability in suicidal ideation**

**Hypothesis 1:** Impaired performance on impulsivity and social threat measures will be associated with higher lifetime rates of suicide attempts, and more severe and more variable suicidal ideation over 24 weeks

**Exploratory:** We will examine these effects by diagnostic group and treatment group assignment

**Supplement Aim 2: Test the accuracy of prediction models with intensive longitudinal data in the two-week window of time before increases in suicidal ideation**

**Hypothesis 2:** Accuracy of our prediction method will be greater than AUC=0.85 in predicting increases and will be greater than that associated with baseline suicide risk

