A subset of 30 Bipolar participants in the EMA-only condition who indicate interest on their consent form (see below) will be approached about obtaining a total of 3 blood draws and cognitive assessments over the first two weeks of the study by participating in two additional encounters. During their in-person session, these participants will undergo the consenting process for these additional procedures, and if they agree to participate, they will immediately be administered the 5 Choice Continuous Performance test of attention and have 5 ml of blood drawn by a trained phlebotomist on staff. Blood pressure will also be measured. This will add one hour to the in-person session for eligible and willing participants. On day 7 (plus or minus 2 days if necessary for scheduling) **Home Visit 1** will occur in the participant's home. A phlebotomist will draw a blood sample of 5 ml, obtain a blood pressure measurement, and administer the 5 choice continuous performance task and digit symbol coding subtest from the MCCB battery. To assess for suicidal ideation, participants will be asked to complete the Columbia Suicide Severity Rating scale. Home Visit 1 is estimated to last 1 hour. On day 14 (plus or minus 2 days if necessary for scheduling) **Home Visit 2** will occur with the same assessments as Home Visit 1. Home Visit 2 is estimated to last 1 hour.

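### Room-temperature storage until assay, with no time limit or run plan, means storage or assay-run error can enter the cytokine variability used in Exploratory Aim 3

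*Protocol*

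**What the plan says.** Protocol section 24 (Biological Materials Transfer Agreement) holds the only handling rule. "Blood will be drawn into a blood collection tube and placed in a biohazard container for transportation"; the phlebotomist delivers it to the laboratory "immediately after visit completion"; and there "the blood samples will be stored at room temperature until assay".

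The draws are described in section 9, under the EMA-only in-person session. The sub-study is "A subset of 30 Bipolar participants in the EMA-only condition". The first draw is at that session, and two home visits follow on day 7 and day 14, each with a window of 2 days either way. At a home visit, "A phlebotomist will draw a blood sample of 5 ml".

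Section 6 gives the purpose. One sentence asks "whether variability in inflammatory markers, mood and cognitive performance predicts future suicide ideation in this population". Exploratory Aim 3 describes a predictive model that includes "inflammatory cytokine levels, and trajectories of negative affect". Cytokines are therefore predictors, used both as a level and as variability within a person. Suicidal ideation is the outcome.

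The SAP covers Hypotheses 1 to 4 only. It has no analysis for Exploratory Aim 3, and so no adjustment for storage time or assay run.

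**The concern.** A variability predictor built from three samples is only as good as the comparability of those samples. Here they are taken about a week apart and the stated storage is unfrozen and open-ended. That leaves two basic ways to assay them. Either one participant's three samples share a run and have stood for different lengths of time, or they are assayed soon after arrival and fall in different runs. In the one case storage time is tied to draw number; in the other, run-to-run error is counted as change in the participant.

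At stake is whether variability in a cytokine means variability in the person. Added error that is unrelated to ideation weakens a real association. Nothing in the plan requires storage time or run to be recorded, so a later analysis might be unable to separate the sources.

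**Working it through.** The plan states no assay error, stability, time to assay or power for this sub-study, so it has no figure to reproduce. The draw timing comes from the protocol. The rest is illustration on assumed values.

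**1. Timing (Protocol section 9).** Draw 1 is at day 0, draw 2 at days 5–9 and draw 3 at days 12–16.
- Draw 1 to draw 2: 5 to 9 days.
- Draw 2 to draw 3: 12 − 9 = 3 to 16 − 5 = 11 days.
- Draw 1 to draw 3: 12 to 16 days.
- Samples: at most 30 × 3 = 90.

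If a participant's three samples are assayed together, these gaps are exactly the differences in storage time.

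**2. Samples held for a shared run.** Assume a constant proportional loss d per day, no true change, and assay at day 14. The day-0 sample then reads (1 − d)^14 of its true value, the day-7 sample (1 − d)^7, and the day-14 sample 1. The spurious CV is the SD of these three values divided by their mean.

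| Assumed loss per day | Day-0 sample reads | Spurious within-person CV |
|---|---|---|
| 0% | 100% | 0% |
| 2% | 75% | 14% |
| 5% | 49% | 35% |
| 10% | 23% | 69% |

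At an assumed 1% per day the day-0 sample reads 87%. All the non-zero rows require a hold of about two weeks, which the protocol does not state.

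**3. Samples assayed on arrival, in separate runs.** The share of apparent within-person variance due to run error is CV_run² / (CV_run² + CV_true²).
- Assumed CV_run 10%, CV_true 40%: 0.01 / (0.01 + 0.16) = 6%.
- Assumed CV_run 10% with CV_true 20%, or 20% with 40%: 0.01 / (0.01 + 0.04) = 20%.
- Assumed CV_run 20%, CV_true 20%: 0.04 / (0.04 + 0.04) = 50%.

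**4. What this does to the variability analysis.** Let k be the error SD divided by the typical true within-person SD, so the three cases in step 3 are k = 0.25, 0.5 and 1. A simulation of 400,000 people took person-specific true SDs as lognormal with log-SD 0.5 and computed the SD of three draws with error added. It gave the correlation between observed and true SD. That figure times an assumed true correlation of 0.5 with ideation is the observable r. Power at n = 30, two-sided 0.05, is Φ(atanh(r) × √27 − 1.96).

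| k | Correlation, observed with true SD | Observable r | Power |
|---|---|---|---|
| 0 | 0.668 | 0.334 | 44% |
| 0.25 | 0.652 | 0.326 | 42% |
| 0.5 | 0.612 | 0.306 | 38% |
| 1 | 0.492 | 0.246 | 26% |

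Even with no artefact, power is only 44%, because three draws estimate an SD poorly.

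**5. What it does to level.** With k now the error SD relative to the between-person SD, the observable r is 0.5 / √(1 + k²). For k = 0, 0.25, 0.5 and 1 this is 0.50, 0.485, 0.447 and 0.354, with power of 81%, 79%, 71% and 48%.

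**The case against.** The strongest reply is that section 24 is a short field in a protocol form and not a laboratory procedure. Delivery straight after the visit fits prompt assay at least as well as a two-week wait, and silence on separation or runs does not show that the laboratory ignores them. That stands as far as it goes. With same-day assay the storage effect is near nil, and at the favourable end of the assumed range run error is only 6% of within-person variance.

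It does not remove the point. The section is not merely silent: it prescribes unfrozen storage with no end point. A laboratory manual that said otherwise would have to be reconciled with it. Prompt assay solves the storage problem by accepting the run problem.

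Three stronger readings are tempting and are not supported:
- A reader might infer that the cytokine values are distorted. The documents give no time to assay, number of runs or stability figure, so distortion cannot be shown, only not excluded.
- A reader might infer a false link with ideation. A drift common to all participants on nearly the same schedule adds a similar trend to everyone. It does not by itself create a link, and it can be adjusted for if storage times are known. A false link would need storage time or run to track ideation as well, and nothing in the documents suggests this. Dilution is the likelier harm.
- A reader might infer damage to the trial's main result. Cytokines do not enter Hypotheses 1 to 4.

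It is also fair to say that handling is not this sub-study's main limit; thirty people with three draws each is.

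**Conclusion.** The point holds as a defect in the stated handling rule. Without frozen storage, draws days apart must differ in storage time, in assay run, or in both, and neither document limits, records or adjusts for either. The consequence is possible error in cytokine level and within-person variability, mainly weakening any association with ideation.

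The size cannot be fixed from the documents. Run error is 6–50% of apparent within-person variance only under the assumed CVs, and the storage figures run from nothing to large depending on a hold time and a loss rate that are both assumed. The scope is one exploratory aim, in up to 30 bipolar participants in one arm. The BPRS primary outcome and the randomized comparisons are unaffected. The change is worth making because it is cheap, and because samples already handled this way cannot be re-processed.

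**What to change.** In Protocol section 24, replace the room-temperature rule with the following:
- on arrival, plasma or serum is separated within a fixed maximum time from the draw, aliquoted and frozen;
- all three samples of a participant are assayed in the same run;
- draw-to-freeze time and run are recorded for every sample.

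Add a short analysis entry for Exploratory Aim 3 that says how both recorded items are used.

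The SAP cover letter says the trial has completed, so samples may already have been kept at room temperature. For these, report storage time and run for each sample, adjust for them, and show the results with and without long-stored samples, using a limit set before the association with ideation is examined. Where a run holds only one sub-study sample, run and true change cannot be separated from these data alone, and the report should say so.

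The cost is one paragraph in the protocol and laboratory instruction, some centrifuge and freezer use, and later results because assays are batched. No extra draws, visits or participants are needed.
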